5.4.2 Anticipated Reactions

Although there are no risks of physical injury, we anticipate that there may be questions in the interview that some study participants find upsetting. However, since study items and topics were chosen to reflect what are likely to be existing concerns, the present study is not expected to markedly increase participants' psychological distress above their routine concerns. Topics covered during the intervention sessions may be emotional, but related distress is expected to be transient and will be supported by a mental health provider. In addition, experienced personnel trained in interviewing medically ill individuals and their families will administer all instruments and will be supervised by the PIs.

All study staff involved in the research are educated on the protection of human research participants and the proposed research will comply with the regulations set forth in 45 CFR Part 46, Protection of Human Subjects. All personnel involved in the proposed protocol have been educated regarding HIPAA regulations and fully understand their responsibility to safeguard the personal health information of every participant involved in the research.

5.4.3 Reaction Management

Any subject participating in the study may decline to continue participation and may withdraw from the study at any time.

Interviewers will be instructed that, should a subject ask about the aims and procedures of the study, they are to describe the project as a study to learn more about supporting surrogate decision-makers of patients in the ICU.

We will collect participants' medical and mental health history, details about outside clinicians, and emergency contact information. Participants will be screened for suicidality based on our screening and management guidelines with the Columbia Suicide Severity Rating Scale embedded²⁰. If research staff identify signs indicating a significant and acute risk of self-harm or harm to others, such information will immediately be shared with the PIs of the study, so that timely and appropriate assessment and care can be provided by a licensed/ board-certified mental health provider or local clinicians when geographically necessary.

Subjects will be assured that all responses will be kept confidential. All of the data collected during the interview process will be de-identified. To ensure confidentiality, data collected will be linked to the participant's personal information only by means of an assigned study identification number. Authorized study staff are the only individuals who have access to the participant's personal information. This information is stored in a password protected computer file for the pilot open trial and secure REDCap data base for RCT/Covid-19 open trial as well as in a locked file cabinet in a locked office. All necessary precautions will be taken to ensure that there is no breach of confidentiality.

There will be only one exception to the strict patient confidentiality policy, described above, which pertains to information obtained during the research assessment or intervention sessions, which would indicate that the participant is seriously suicidal and may pose a significant and acute risk of self-harm or harm to others. Participants will be informed of this exception, and will also be informed that such information will be shared with the PIs of the study so that timely and appropriate psychiatric assessment and care can be provided. If a participant at acute risk of self-harm (endorses items 3 of the Columbia Suicide Severity Rating Scale) or harm to others cannot be reached by the study team within 3 hours (after at least two phone call attempts and an email requesting a call back), the participant's emergency contact(s) will be contacted. If a participant endorses passive but not acute suicidal ideation (i.e. endorses items 1 or 2 but not item 3 of the Columbia Suicide Severity Rating Scale) and is unable to be contacted by the research team in a timely manner, emergency contacts will be contacted at the discretion of the study mental health professionals based on their clinical judgment. If an acutely distressed individual who denies active suicidality or homicidality cannot be reached within 24 hours (after at least two phone call attempts and an email requesting a call back), the participant's emergency contact(s) will be contacted. These details are outlined in the informed consent.

6.1 Statistical Analysis

6.2 Data Management

Data will be entered into a secured REDCap database and stored on the WCM server. The PI and staff will review data entry regularly and within the first month, responses will be reviewed for distributions and to address concerns identified by respondents. Any necessary changes to ensure data quality or integrity will be submitted to the IRB as an amendment and modifications made to the REDCap database following IRB approval.

6.1 Data Analysis Plan

Below are descriptions of the statistical procedures performed to test each of the hypotheses. Participant data will be stored in a locked file cabinet and using a secured REDCap database. Missing data will be estimated using a multiple imputation procedure described by Schafer and Olsen³⁷. There will not be a data monitoring committee due to the trial's relatively short duration and the minimal risks the intervention poses. Trial data will

not be independently audited. An interim analysis of the pilot data will occur to inform the conduct of the randomized control and edits to the EMPOWER manual. Data for participants who come bereaved before the administration of EMPOWER or EUC interventions will be treated as exploratory and analyzed separately.

Specific Aim #1: Develop EMPOWER for surrogate decision-makers of critically ill patients who at risk of becoming unable to communicate and/or are currently are unable to communicate in the ICU.

There are no hypotheses for this aim. We will use thematic content analysis, a well-established, systematic qualitative analysis approach in health research, to identify themes from stakeholder participants' narratives and exit interviews. We will follow Morse's²¹ guidelines for conducting rigorous qualitative research (e.g., audit trail, saturation) using Atlas.ti software. We will independently review each interview transcript as well as qualitative data gathered from manual edits and Delphi survey responses and will synthesize and interpret participants' feedback about the content of the EMPOWER manual.

Specific Aim #2: Determine the feasibility, tolerability, acceptability, and preliminary effects of EMPOWER on surrogate decision-maker mental health.

We will compute descriptive statistics to characterize the feasibility and acceptability of EMPOWER by examining helpfulness/satisfaction ratings, rates of recruitment, reasons for refusal, and number of modules/booster calls completed. Targets will include completion of 4/6 modules for feasibility and tolerability. Target acceptability will be an average score greater than 3 on the acceptability items in the post-intervention satisfaction questionnaire among participants who received EMPOWER. Tolerability will also be measured by open ended-responses to qualitative questions asked at T4 regarding negative experiences, emotional difficulties, and perceived costs and benefits of participating in the intervention. Drop-out will not be considered as a metric of tolerability due to the highly stressful and variable circumstances of ICU caregiving, unless participants drop out of the study and specifically express that they consider it to be too distressing. Qualitative data analysis will be used to analyze data from open-ended questions to identify the most helpful components of EMPOWER.

To evaluate the preliminary effects of EMPOWER among participants in the combined RCT and COVID-19 open trial phases, we will use a hierarchical linear modeling (HLM) and an intent-to-treat approach. HLM is statistically appropriate because of the clustering within interventionists and within surrogate decision-makers. HLM will correct for this clustering by modeling interventionists and surrogate decision-makers as random effects, as has been done in prior trials ^{38 39}. This will also provide a treatment assignment model coefficient and effect size estimate for our future, larger study.

HLM modeling will determine differences between surrogate decision-makers and patients assigned to EMPOWER vs. enhanced usual care. The primary outcome is post-intervention (T2) differences in PDI scores. Secondary outcomes are differences in scores on the PGD 12/13 and BEAQ at one-month (T3) and three-month (T4) follow up from T2. Exploratory outcomes are differences in scores on the IES-R, STAI, PHQ-9 and Decision Regret Scale at one-month (T3) and three-month (T4) follow up. HLM models will include covariates, either as fixed-effect or time-varying, if those variables are found to be significantly statistically associated with both intervention assignment and the outcome examined.

Specific Aim #3: Examine the effects of EMPOWER on patient outcomes in the month following the ICU admission.

Logistic regression models will regress patient quality of life or quality of death (depending on whether the patient survives or dies in the observation period) for EMPOWER versus enhanced usual care condition. Logistic regression analyses will model the effects of EMPOWER on the odds of patients receipt of value-concordant care (i.e., surrogate baseline assessment of patient preferences regarding quality of life versus quantity of life matched with receipt of intensive life-prolonging procedures/palliative care).

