1.1 Overview

To obtain stakeholder input on EMPOWER and refine the intervention manual, we propose to enroll up to 10 bereaved caregivers of patients who were incapacitated and treated in the ICU and 10 clinicians with expertise in ICU and/ or mental health care to have them review the study protocol and intervention manual and to obtain structured feedback on EMPOWER. Interviews will be audio-recorded, transcribed verbatim by trained staff, and kept confidential. Participants will also have the option to respond to interview questions through written response. In addition, we will enroll family caregivers and ICU patients to pilot the EMPOWER intervention and examine its effects on both informal caregivers and patients in the ICUs at New York Presbyterian Hospital (NYPH)- Weill Cornell, New York Presbyterian Hospital-Queens, and Memorial Sloan Kettering Cancer Center (MSK), as well as among surrogate decision-makers from outside hospitals recruited online. Surrogate decision-makers will be screened for emotional dependency on the patient and feelings of emotional distress related to the patients' ICU admission. Eligible surrogate decision-makers will be enrolled. The first 10 surrogate decision-makers will be enrolled in an open trial. A pilot RCT will then begin, randomizing surrogate decision-makers to receive either EMPOWER or enhanced usual care using a block-randomization strategy to determine condition assignment., A second open trial phase, only assigning surrogates to the EMPOWER trial in response to the COVID-19 pandemic, began on April 2020, with a return to the RCT following approval of amendment #1610017622-13. 60 surrogate decision makers will be enrolled in the RCT and COVID-19 open trial phases combined. Surrogate decision-makers will be assessed at 4 time points (T1 = baseline, T2 = up to one week following intervention, T3 = one month from T2, and T4 = three months from T2). The EMPOWER intervention will be administered by trained interventionists either in-person or via telehealth. The intervention sessions will be audio-recorded for training purposes. If participants agree, the sessions will be video-recorded. Patients' medical chart information will be abstracted

following the death of the patient. If the patient is not deceased by the end of their surrogate decision-maker's participation in the study, medical chart information will be abstracted at T4.

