Surrogate decision-makers will be assessed pre-intervention/baseline (Time point 1, T1), post-intervention (within a week of the surrogate decision-maker's completion of the baseline assessment) (Time point 2, T2), 1-months after post-intervention assessment (Time point 3, T3), and 3-months after post-intervention assessment with an additional exit interview with the research staff that will take about 40 minutes to complete for those receiving EMPOWER only (Time point 4, T4). Assessments will be completed using paper-and-pencil assessments, over the phone with research staff, or online (REDCap). The exit interview will be audio recorded and can be in person, over the phone, or over videoconference.

The EMPOWER arm includes 6 modules that are approximately 15-20 minutes each, all delivered by the same interventionist one-on-one in person or if needed, over the phone or video conference. The intervention can be completed in approximately 1.5 to 2 hours in a single sitting in the ICU, or modules can be completed in piecemeal if the surrogate decision-maker prefers or needs to stop because of, for example, the need to attend to the patient or speak with the medical team. If the intervention is completed in piecemeal, it is expected the intervention will occur over the course of 2-3 days, although scheduling will be flexible to not burden participants and be sensitive to needs such as bereavement and urgent medical situations. There are 2 booster sessions (approximately 1 hour each) that are conducted via telehealth medium such as phone or video call 2 and 4 weeks after the initial 6 modules are completed. If the patient dies before the 6 modules are completed, the interventionist will make a condolence call during which he/she will offer to continue the modules if the surrogate decision-maker is interested (during that call or at a separate time). If the surrogate decision-maker declines completion of the 6 modules, the interventionist will indicate that he/she will call again in 2 weeks to offer support and review what they have previously discussed. Due to the wide variety of

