Adult Surrogate Post-intervention Assessment (T2): PG-12 (if patient is alive); FOLLOS (if patient is alive); PG-13 (if patient is deceased); ²⁴ ^{25,26} PDI; PDEQ; IES-R; BEAQ; STAI; DTS revised version; Caregiver Self-Efficacy in the ICU Scale; DRS - EMPOWER; Regret Assessment; Post-Intervention Satisfaction Questionnaire (PISQ).

Adult Surrogate 1 Month Post-T2 Assessment (T3): PG-12 (if patient is alive); FOLLOS (if patient is alive); PG-13 (if patient is deceased); PDI; IES-R; BEAQ; STAI; PHQ-9; DTS revised version; Critical Care Family Satisfaction Survey- EMPOWER; CEQUEL-R (if patient is alive); CEQUEL ²³ (if patient is deceased); Quality of Life (if patient is alive); Quality of Death (if patient is deceased); DRS - EMPOWER; Regret Assessment; Medical Information Update

Adult Surrogate 3 Months Post-T2 Assessment (T4): PG-12 (if patient is alive); FOLLOS (if patient is alive); PG-13 (if patient is deceased); PDI; IES-R; BEAQ; STAI; PHQ-9; DTS revised version; CEQUEL-R (if patient is alive); CEQUEL (if patient is now deceased, but was alive at T3); Quality of Life (if patient is alive); Quality of Death (if patient is deceased); DRS - EMPOWER; Regret Assessment; Medical Information Update; Qualitative Exit Interview for (participants receiving EMPOWER intervention only).

Pediatric Surrogate Assessments: STAI, PDI, PG-12, IES-R, DRS-EMPOWER at all 4 timepoints, with brief demographics at T1, Post-Intervention Satisfaction Questionnaire at T2, and Qualitative Exit Interview at T4 (for participants receiving EMPOWER intervention only).

Measure Title	Time Points Used*	Description of Measure
McGill Quality of Life Scale	Screener	Items 5 through 8 are used to measure anxiety/depression.
Partner Dependency Scale (PDS)	Screener	Items 1 and 2 of the PDS are used to measure dependency. The language is altered to refer to the patient rather than a spouse.
Columbia Suicide Severity Rating Scale	Screener	Items 1 and 2 of the CSSRS are used to measure suicidal ideation.
Peritraumatic Distress Inventory (PDI) ICU Version	T1, T2, T3, T4	Measures peritraumatic distress.
Peritraumatic Dissociative Experiences Questionnaire (PDEQ) ICU Version	T1, T2	Measures experiences of dissociation that may occur in the ICU. Instructions are changed to prompt the participant to specifically answer the survey in reference to their experience in the ICU.
Impact of ICU Events Scale- Revised (IES-R)	T1, T2, T3, T4	Measures symptoms of PTSD.

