Fears of Losing Loved Ones Scale (FOLLOS)	T1, Status dependent @ T2, T3, T4	Measures attachment-related distress associated with anticipatory grief. Items were developed by clinicians and an expert in psychometrics.
Caregiver Evaluation of the Quality of End-of-Life Scale (CEQUEL)	Status dependent @ T3, T4	Measures caregiver's subjective evaluation of the patient's quality of death. If administered at T3 due to patient death, will not be administered at T4.
CEQUEL-Revised	Status dependent @ T3, T4	Administered to caregivers whose patients are still living. Retains items measuring caregiver satisfaction with medical care for the patient, but removes questions regarding patient's death.
CEQUEL-Revised	Status dependent @ T3, T4	Administered to caregivers whose patients are still living. Retains items measuring caregiver satisfaction with medical care for the patient, but removes questions regarding patient's death.
Quality of Life/Death	Status dependent @ T3, T4	Measures caregiver's perception of the patient's most recent week of life (either their most recent week, or most recent week before death). If Quality of Death is administered at T3, it will not be administered again at T4. Items have been previously published upon and validated ² .

^{*}Refers to assessments for adult surrogate participants

Qualitative data:

All surrogate decision-makers will provide feedback on the intervention in a post-intervention satisfaction questionnaire at T2. Those assigned to the EMPOWER intervention will also participate in a qualitative exit interview at T4. Stakeholders will provide feedback on the intervention manual in self-report questionnaires, written form, and/or in-person interviews. Clinicians will provide information about the patient before recruitment occurs via the patient information form or discussion with research assistants.

5.2 Data Collection (Please find the details on data to be collected in 5.2)

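### The numeric acceptability target is scored only at T2, before either booster session, so it reflects the six modules and not the full EMPOWER package

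*Combined protocol and SAP*

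**What the plan says.** Section 6.1 (Data Analysis Plan, Specific Aim #2) gives the criterion: "Target acceptability will be an average score greater than 3 on the acceptability items in the post-intervention satisfaction questionnaire among participants who received EMPOWER". The same paragraph sets a feasibility and tolerability target of 4 of 6 modules. It lists booster calls among the things to be counted, without a target. It also assigns open-ended T4 questions to tolerability.

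Section 5.1 (Measures Used) fixes when the questionnaire is given: "All surrogate decision-makers will provide feedback on the intervention in a post-intervention satisfaction questionnaire at T2". The pediatric battery agrees: "Post-Intervention Satisfaction Questionnaire at T2, and Qualitative Exit Interview at T4". The adult T3 and T4 batteries do not contain it.

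Section 5.2 (Study Design) describes the content: "The EMPOWER arm includes 6 modules that are approximately 15-20 minutes each", and then "There are 2 booster sessions (approximately 1 hour each"), held "2 and 4 weeks after the initial 6 modules are completed".

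T2 is defined twice. Section 5.2 has "post-intervention (within a week of the surrogate decision-maker's completion of the baseline assessment"). Section 1.1 (Overview) has "T2 = up to one week following intervention".

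**The concern.** The measures table in section 5.1 says the acceptability items draw on constructs such as burden, opportunity cost and perceived effectiveness. Two further one-hour sessions could change answers on each of these, and by then some surrogates will be bereaved. Participants nevertheless answer before either session has taken place.

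The pilot is meant to inform a larger efficacy trial of EMPOWER. Its secondary outcomes are measured at T3 and T4. On the usual timing both boosters are due by T3, so those effect estimates would describe modules plus boosters while the acceptability score describes modules alone. Both stated numeric targets, 4 of 6 modules and a mean above 3, could be met with no booster delivered.

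**Working it through.** **Inputs.** All come from section 5.2 unless noted.
- Modules: 6, at 15 to 20 minutes each.
- Boosters: 2, at about 60 minutes each, due on days 14 and 28 after the modules.
- T2: within 7 days of baseline (section 5.2), or up to 7 days after the intervention (section 1.1).
- T3 and T4: one and three months after T2, taken here as 30 and 90 days.

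**Plan's own figure.** 6 × 15 = 90 minutes and 6 × 20 = 120 minutes. This reproduces the 1.5 to 2 hours that section 5.2 gives for the modules.

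**Share of planned contact time delivered by T2.** Share = modules / (modules + boosters), with boosters = 2 × 60 = 120 minutes.
- Shorter modules: 90 / (90 + 120) = 90/210 = 42.9%.
- Longer modules: 120 / (120 + 120) = 120/240 = 50.0%.

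The boosters are therefore the other 50% to 57%. A participant who just meets the 4-of-6 target has had 60 to 80 minutes by then, which is 60/210 = 28.6% to 80/240 = 33.3% of the full plan.

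**Does T2 precede the boosters?**
- Section 5.2 anchor: the modules follow baseline, so a T2 within 7 days of baseline is at most 7 days after the modules end. Booster 1 is at least 14 − 7 = 7 days later and booster 2 at least 28 − 7 = 21 days later.
- Section 1.1 anchor, with the intervention read as the six modules: the same gaps of at least 7 and 21 days.
- Section 1.1 anchor, with the boosters included: T2 would fall on day 28 or later, which contradicts section 5.2.

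**Where a later score could sit.** If T2 falls 0 to 7 days after the modules, T3 falls on about days 30 to 37. That is only 30 − 28 = 2 to 37 − 28 = 9 days after booster 2 is due. If the modules run past a T2 tied to baseline, or booster 2 is late, T3 can come first. T4 falls on about day 90 or later, at least 90 − 28 = 62 days after booster 2 is due.

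**The case against.** The strongest reply is that the plan often uses the word intervention for the six modules alone. Section 5.2 says it can be finished in one sitting, section 1.2 speaks of about 90 minutes in total, and T2 is named the post-intervention assessment and carries the primary outcome. On that usage, scoring acceptability at T2 is coherent. This explains the choice but does not close the gap. Section 6.1 counts booster calls when it characterises EMPOWER's feasibility and acceptability, so the plan treats boosters as part of the package. If the target is meant for the modules only, the protocol should say so.

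A reader might infer that the boosters go unassessed. The documents do not support that. Uptake will be described, and EMPOWER participants are asked at T4, when both boosters are due, about bad experiences, emotional strain, and what taking part cost and gave them. Those topics overlap with the acceptability constructs. What is missing is only a scored measure after the boosters.

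A reader might also infer that meeting the target would wrongly trigger a larger trial. Section 6.1 ties no go/no-go decision to it. It stands beside satisfaction ratings, recruitment, refusals, session counts and interviews. Nor do the documents suggest that participants will find the boosters burdensome.

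Finally, section 5.3.1 lets assessments slip around major events, so an individual T2 could follow a booster. That is an exception and not a planned measurement.

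**Conclusion.** The point holds in a limited form. As scheduled in section 5.2, the only numeric acceptability target is answered at least 7 days before booster 1 and at least 21 days before booster 2, when about 43% to 50% of planned contact time has been delivered. A mean above 3 would support the acceptability of the six modules. It would not by itself support the acceptability of modules plus boosters. This narrows one Aim 2 conclusion and does not undermine the trial.

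The percentages rest on approximate planned session lengths, on all six modules being given (section 5.2 lets the interventionist omit parts), and on T2 preceding the boosters. They measure planned time, not how much each part matters to participants.

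**What to change.** 1. Repeat the acceptability items once, after both boosters are due. T4 is the simplest place, beside the existing exit interview. T3 would serve only where booster 2 has already been completed or declined.
2. Ask everyone who received EMPOWER, including those who declined one or both boosters. Restricting the items to booster attenders would drop the people likely to find the boosters least acceptable and would tend to raise the mean.
3. Report the T2 score (modules) and the later score (full intervention) separately against the existing threshold of above 3. Show results by number of boosters completed (0, 1 or 2), with the number answering at each time.
4. If the items are not repeated, add one sentence to section 6.1 limiting the acceptability conclusion to the six modules.
5. Reconcile the two T2 definitions in sections 1.1 and 5.2.

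The cost is a few extra minutes at one existing assessment for EMPOWER participants, plus an amendment. T4 has two drawbacks: recall of the boosters over about two months, and possible drop-out between T2 and T4. The item wording is not in the documents, so its suitability for a later administration needs checking. Option 4 adds no participant burden.
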